### 6.3 PATIENT SETS ANALYSED

The safety set and the effectiveness set are defined as follows. The safety set will be the basis of all demographic, baseline and safety analyses. Effectiveness analysis will be on basis of the effectiveness set.

- Safety set:  
This patient set includes all patients who had no invalid registration, who were documented to have taken at least one dose of TRADIANCE®.
- Effectiveness set:  
This patient set includes all patients with TRADIANCE® in the safety set who have a baseline and at least one available on-treatment HbA1c or FPG value.

[figure not shown]
## **6.5 POOLING OF CENTRES**

This section is not applicable because centre/country is not included in the statistical model.

## **6.6 HANDLING OF MISSING DATA AND OUTLIERS**

If only year of date is non-missing, then missing date are imputed 01 JUL of reported year. Else if only year and month of date are non-missing, then missing date is imputed 15 of the reported months.

Safety:

Effectiveness:

Missing effectiveness data will not be imputed.

Date of last TRADIANCE® intake:

To calculate duration of TRADIANCE® treatment at an interim analysis, the date is imputed with the date of the snapshot.

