9.7.1 Analyses of Safety

[figure not shown]
The safety analysis will include all patients who registered in the study and receiving the TRADIANCE® Combination Tablets AP or BP treatment at least one time except those who are found to have no observation after enrolment, invalid registration, or invalid contract with the site (see section 9.7). In general, safety analyses will be descriptive, based on BI standards, and focus on AEs related to the TRADIANCE® Combination Tablets AP or BP treatment.

Proprietary confidential information © 2018 Boehringer Ingelheim International GmbH or one or more of its affiliated companies

AEs will be coded using the current version of the Medical Dictionary for Drug Regulatory Activities (MedDRA) and will be based on the concept of treatment emergent AEs. To this end, all AEs occurring between the initiation of TRADIANCE® Combination Tablets AP or BP prescribed at baseline visit and 7 days (inclusive) after the last administration will be considered 'treatment emergent'. An AE is considered to be an ADR if either the physician/investigator who has reported the AE or the sponsor assesses its causal relationship as 'related'.

The frequency of ADRs will be tabulated by system organ class and preferred term according to the current MedDRA version. The frequency of SAEs will also be tabulated likewise. The incidence of ADRs stratified based on patient demographics will also be investigated.

No imputation is planned for missing AE data except for missing onset dates which will be handled according to BI standard.

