**4. CHANGES IN THE PLANNED ANALYSIS OF THE STUDY**

No change has been made in the planned analyses from the statistical methods described in the NIS Protocol.

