## **6. GENERAL ANALYSIS DEFINITIONS**

### **6.1 TREATMENT(S)**

For basic study information on treatments, please refer to NIS Protocol Section 4. The technical specification for treatment set-up is described in the analysis data set (ADS) plan.

For effectiveness analyses, data up to 7 days after last treatment intake will be considered as on treatment for HbA1c and 1 day for FPG. For safety analyses, data up to 7 days after last treatment intake will be considered as on treatment for AE, 1 day for weight, blood pressure and pulse and 3 days for laboratory measurements.

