### **7.8.1 Adverse events**

Unless otherwise specified, the analyses of adverse events will be descriptive in nature. All analyses of AEs will be based on the number of patients with AEs and NOT on the number of AEs.

For further details on summarization of AE data, please refer to the guideline “Analysis and Presentation of Adverse Event Data from Clinical Trials” ([3](#)).

AE analyses will be carried out after integrating AE data from CRF and AE data from perceive system. In addition, AEs coded as “no adverse event” will not be included in the AE analyses.

The analysis of adverse events will be based on the concept of treatment emergent adverse events. That means that all adverse events occurring between first drug intakes till 7 days after last drug intake during observation period will be analysed. For details on the treatment definition, see [Section 6.1](#).

An overall summary of adverse events will be presented.

The frequency of patients with AEs, severe AEs, drug related AEs, AEs leading to discontinuation, drug related AEs leading to discontinuation, outcome for serious AEs and outcome for serious drug related AEs are tabulated.

The frequency of patients with AEs, ADRs, SAEs and SADRs will be summarised by primary system organ class and preferred term. Patients with ‘priority survey items’ according to the drug’s Risk Management Plan will be summarised separately. The analysis of “priority survey items”, “Important identified risks”, “Important potential risks” will be conducted for AEs, ADRs.

It is created that table of patient with ADRs in each subgroup defined in [Section 6.4](#). Not only the frequency but also the odds ratios are displayed.

In addition summaries for the time to onset of first episode for the ADRs will be tabulated, by duration (<= 12 week, 12 to <=26 weeks, 26 to <=52 weeks, > 52), by primary system organ class and preferred term.

Adverse events leading to death and adverse events leading to discontinuation will be also summarised by treatment, primary system organ class and preferred term.

An ADR is defined as an AE for which either the investigator or the sponsor (or both) assess the causal relationship to TRADIANCE® as “Yes”. A SAE is defined as an AE for which either the investigator or the sponsor (or both) assess the seriousness either as “Serious”.

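### SAP 6.6 sets partial dates to mid-month or 1 July with no bound by first or last dose, so a partly dated ADR can be put on the wrong side of the treatment-emergent window; the effect on overall incidence is probably small

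*SAP*

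**What the plan says.** SAP 6.6 opens with a general rule for partial dates. With the year alone: "If only year of date is non-missing, then missing date are imputed 01 JUL of reported year". With year and month: "Else if only year and month of date are non-missing, then missing date is imputed 15 of the reported months". The rule stands above the sub-headings and names no variable. The only special rule for last intake concerns interim reports: "To calculate duration of TRADIANCE® treatment at an interim analysis, the date is imputed with the date of the snapshot".

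The window that these dates feed is in SAP 7.8.1: "all adverse events occurring between first drug intakes till 7 days after last drug intake during observation period will be analysed". SAP 6.1 agrees: "data up to 7 days after last treatment intake will be considered as on treatment for AE". The primary outcome, ADR incidence, is analysed within that window (SAP 7.4 and 7.8).

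Protocol 9.7.1 has its own statement on adverse event dates: "No imputation is planned for missing AE data except for missing onset dates which will be handled according to BI standard". That standard is not reproduced. SAP section 4 declares: "No change has been made in the planned analyses from the statistical methods described in the NIS Protocol".

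**The concern.** A fixed mid-point is harmless for a diagnosis date. It is not harmless for a date that decides whether an event falls inside a window with hard edges. Two dates do this here.

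- **Last intake.** A patient stops on 27 June and the site records only June. Last intake becomes 15 June and the window closes on 22 June. An ADR with an exact onset of 25 June, perhaps the reason for stopping, is excluded.
- **Onset.** A patient starts on 20 March 2019 and has an ADR on 25 March, recorded as March 2019. Onset becomes 15 March, before first dose, and the ADR is excluded if this rule governs onset.

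The events most exposed are early ADRs and ADRs around discontinuation, which a safety surveillance most needs to capture. SAP 7.8.1 also tabulates events leading to discontinuation and time to first ADR, and plans a rate per 100 patient-years. All of these use the same dates.

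**Working it through.** The plan states no figure on partial dates, so there is none to reproduce.

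**Inputs from the documents.** The rule in SAP 6.6; the window of first intake to last intake + 7 days (SAP 6.1, 7.8.1); registration from January 2019 to January 2020 (Protocol 9.2.2.2), with data collection starting on 15 January 2019 (Protocol 6); follow-up of up to 52 weeks (Protocol 9.3.1).

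**Assumptions.** First doses are uniform from 15 January 2019 to 31 January 2020. Onset patterns are as stated in each step. Every simulated ADR is truly inside the window. All loss percentages are conditional on the date being partial.

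**1. Month-only stop date, exact onset.** Imputed last intake is the 15th, so the window closes on the 22nd. An ADR k days before a stop on day d is lost if d − k > 22. With an average month of 30.44 days and d uniform:

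| k (days before stop) | Lost if d is after the | Share lost |
|---|---|---|
| 0 | 22nd | 8.44/30.44 = 28% |
| 3 | 25th | 5.44/30.44 = 18% |
| 7 | 29th | 1.44/30.44 = 5% |
| 14 | never | 0% |

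Simulation gives the same values. For year-only stop dates it gives 44% to 48% over the same four lags.

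**2. The opposite error.** An exact onset 8 days after the stop is truly outside the window. It is counted if d + 8 ≤ 22, that is d ≤ 14: 14/30.44 = 46%. So the rule also pulls events in.

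**3. Month-only onset, if SAP 6.6 governs it, treatment completed to 52 weeks.** The event is classed as pre-dose when first dose is after the 15th and onset falls in the same month. For a 31-day month and onset uniform over w days, the share is (1 + 2 + … + 16)/(31w) = 136/(31w):

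- w = 28: 136/868 = 15.7%; simulated over all months, about 15%.
- w = 84: 136/2604 = 5.2%; simulated, about 5%.
- w = 364: 136/11284 = 1.2%; simulated 1.2%, plus 0.2% lost at the far end, 1.4% in total.

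**4. Month-only onset, drug stopped on the day of the ADR, stop date exact.** Onset on the 15th lies beyond d + 7 when d is 1 to 7: 7/30.44 = 23%. Adding the pre-dose losses, the simulated total is 24% to 37%, depending on how early ADRs occur.

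**5. Year-only onset.** Simulated loss is 23% to 44% with treatment completed, and 60% to 94% when the drug is stopped at the ADR.

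**6. Bounding.** With imputed onset held between first intake and last intake + 7 days, loss is 0% in every onset scenario.

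**7. Effect on overall incidence through onset dates.** Assume 10% ADR incidence in 1000 patients and 5% of ADRs partly dated: 1000 × 0.10 × 0.05 = 5 patients at risk.

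- All month-only: 5 × 0.014 = 0.07 to 5 × 0.373 = 1.9 patients, or 0.01 to 0.19 points.
- All year-only: 5 × 0.233 = 1.2 to 5 × 0.942 = 4.7 patients, or 0.12 to 0.47 points.

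For comparison, the 95% confidence half-width at 10% is 1.96 × √(0.10 × 0.90/1000) = 1.9 points.

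**8. Effect through stop dates.** If 5% of stop dates are month-only, 0.05 × 18% to 28% = 0.9% to 1.4% of ADRs with onset 3 to 0 days before the stop are lost. At 20% the figure is 3.6% to 5.6%.

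**9. Exposure.** A patient who starts on 10 September 2019 and stops that November, with only 2019 recorded, gets a last intake of 1 July, before first dose. With stops spread over days 15 to 363 (assumed), about 11% of year-only stop dates give such negative exposure.

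**The case against.** A reader might infer that the plan definitely removes ADRs from the primary outcome. The documents do not support that.

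- **Onset may follow another rule.** Protocol 9.7.1 is specific to onset dates and sends them to a company standard, from which the SAP declares no departure. SAP 7.8.1 adds: "For further details on summarization of AE data, please refer to the guideline". The entry under Safety in SAP 6.6 is empty in the public copy, and text may have been removed there; this is not counted against the plan. The onset limb therefore stays conditional.
- **Last intake may be specified elsewhere.** SAP 6.1 leaves the technical treatment set-up to the analysis data set plan, which is not public, and Protocol 9.3.1 allows final contact as the end of exposure. This lowers confidence. Still, the protocol's reference to the company standard covers onset dates only, and no document in hand overrides the printed rule for a partial stop date at the final analysis.

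Two further inferences also fail. One is that a vague date can only lose events; step 2 shows that it can also add them, and if onset and stop are both month-only in the same month, both become the 15th and the ADR is kept. The other is that partial dates must be common because the sponsor has no direct access to source records (Protocol 9.10.2.2). That makes them harder to resolve but does not create them. The protocol collects start and end dates, asks for immediate entry of adverse events, and follows ADRs until resolved or sufficiently characterised.

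**Conclusion.** The point holds in a limited form. As printed, the rule has no bound by dose dates. It gives wrong classifications for some partial last-intake dates, and for some partial onset dates if no other standard applies. The losses are substantial among the affected records near the start or stop of treatment, but most month-only ADRs stay correctly inside the window.

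The effect on overall ADR incidence is probably small: roughly 0.01 to 0.5 percentage points, against a confidence half-width of 1.9 points. That range rests on an assumed 10% incidence and 5% of ADRs partly dated; neither figure is in the documents. It would scale up with a larger share. Tables of ADRs leading to discontinuation and of early onset could be affected proportionately more. Severity is minor and confidence moderate.

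**What to change.** Amend SAP 6.6 as follows.

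1. State which rule governs AE onset dates and reconcile it with Protocol 9.7.1.
2. Class an AE as treatment-emergent unless the known part of its onset date, its end date or the known dose dates rule this out. Equivalently, bound an imputed onset by first intake and last intake + 7 days.
3. For the treatment-emergent flag only, take a partial last-intake date as the latest date consistent with what was reported, capped at last contact or end of observation.
4. For exposure and person-years, keep the mid-point, bounded below by first intake and above by last contact. Using the latest possible date here would inflate the denominator of the rate per 100 patient-years.
5. Report how many ADRs are treatment-emergent only through imputation.

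The cost is a few sentences and a few lines of code. The downside is that a few events just outside the window may be counted; item 5 shows how many.

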4. ABSTRACT

Name of company: Boehringer Ingelheim			
Name of finished medicinal product: TRADIANCE® Combination Tablets AP, BP			
Name of active ingredient: Empagliflozin, Linagliptin			
Protocol date: 8 December 2017	Study number: 1275.0026	Version/Revision: Version 2.0	Version/Revision date: 20 November 2018
Title of study:	Post Marketing Surveillance in Japan on Long Term Drug Use of TRADIANCE® Combination Tablets AP and BP in Patients with type 2 Diabetes Mellitus		
Rationale and background:	
In Japan, post-approval execution of Post Marketing Surveillance is requested by the Japanese Pharmaceuticals and Medical Devices Act (J-PMD Act) in order to accumulate safety and efficacy data for re-examination. Re-examination period is defined by J-PMD Act. Four years after approval of combination drugs, results of PMS need to be submitted as a part of re-examination dossier to the Japanese regulatory authority, the Ministry of Health, Labour and Welfare (MHLW).
 
Collected data from PMS will be included in the Japanese periodic safety reports and submitted to MHLW on designated dates until the end of re-examination period.
		
Research question and objectives:	Study objective is to investigate the safety of long-term daily use of TRADIANCE® Combination Tablets AP and BP in Japanese patients with type 2 Diabetes Mellitus under real-world use.		
Study design:	
Cohort study
 
Non-interventional, single arm study based on newly collected data
 
Patients will be observed for up to 52 weeks after start of the treatment with TRADIANCE® Combination Tablets AP or BP or until discontinuation of administration.
		
Population:	
Inclusion criteria
 
- Japanese patients with type 2 Diabetes mellitus who are prescribed with TRADIANCE® Combination Tablets AP or BP- Patients who have never been treated with TRADIANCE® Combination Tablets AP or BP before enrolment 
Exclusion criteria
 
None
		

Name of company: Boehringer Ingelheim			
Name of finished medicinal product: TRADIANCE® Combination Tablets AP, BP			
Name of active ingredient: Empagliflozin, Linagliptin			
Protocol date: 8 December 2017	Study number: 1275.0026	Version/Revision: Version 2.0	Version/Revision date: 20 November 2018
Variables:	
Outcomes: Primary outcome: Incidences of adverse drug reactions (ADRs)
 
Secondary outcomes: None
 		

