9.3 VARIABLES

9.3.1 Exposures

Exposure to TRADIANCE® Combination Tablets AP or BP is estimated as time from the day TRADIANCE® Combination Tablets AP or BP is initiated until the day the drug is last administrated on a patient-level (or the final contact with the patient during the regular observation period).

Patients newly initiating TRADIANCE® Combination Tablets AP or BP will be followed up to 52 weeks.

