9.7.3 Interim analyses

Several interim analyses will be performed for the purpose of submission of periodic safety reports to PMDA (Pharmaceuticals and Medical Devices Agency) in project (status update of using TRADIANCE® Combination Tablets AP and BP not only with this study but all usage, every 6 month in two years after approval and every 12 months afterward. The submission date is depending on the time from the approval).

Final results will be submitted in the re-examination dossier to PMDA by 25 March 2023.

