## **7.7 EXTENT OF EXPOSURE**

Only descriptive statistics are planned for this section of the report.

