The system organ classes will be sorted according to the standard sort order specified by EMA, preferred terms will be sorted by frequency (within system organ class).

The following AEs are detected on the basis of the Standardised MedDRA queries (SMQs) or Boehringer Ingelheim customised MedDRA query (BICMQ) (details are described in ADS plan).

Safety will be assessed by treatment exposure time adjusted incidence rate (n in 100 patient years) of ADRs.

Important identified risk, Important potential risk and significant ADRs.

The following AEs are summarised on the basis of the Standardised MedDRA queries (SMQs) or Boehringer Ingelheim customised MedDRA query (BICMQ) by primary SOC and PT.

\*: ADRs are also summarised.

Important identified risks

- Urinary tract infection \*
- Genital infection \*
- Volume depletion \*
- Hypoglycaemia \*
- Pancreatitis \*
- Ketone body increase/Ketoacidosis \*
- Polyuria/Pollakiuria \*
- Intestinal obstruction \*
- Hepatic function disorders \*

Important potential risks

- Renal disorder \*
- Bone fracture \*
- Skin lesion \*
- Bullous pemphigoid \*
- Interstitial pneumonitis \*
- Infection \*
- Malignant tumour \*
- Cardiac failure \*
- Influence of weight decreased on safety \*
- Lower limb amputation \*

Risk ratios with 95% confidence intervals will be shown for subgroup analysis. In case that there will be the significant difference each factor, the frequency of patients with ADRs and with serious AEs will be summarized by primary SOC and PT. Due to the high number of exploratory subgroup analyses, it is recognised that the likelihood of chance findings is high and therefore subgroup results should be interpreted with caution.

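### At late interims, SAP 6.6 sets an undated last intake to the snapshot date with no week-52 limit, so exposure can run past the observation period and dilute any ADR rate per patient-year

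*SAP*

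**What the plan says.** SAP 6.6, under the date of last intake: "To calculate duration of TRADIANCE® treatment at an interim analysis, the date is imputed with the date of the snapshot". The visible text gives no upper limit.

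The passages on follow-up and exposure are:
- Protocol abstract, study design: "Patients will be observed for up to 52 weeks after start of the treatment", or until discontinuation.
- Protocol 9.3.1 ends exposure at the last administration, with a bracketed alternative: "or the final contact with the patient during the regular observation period". The same section sets follow-up at up to 52 weeks.

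The passages on what the exposure time is used for are:
- SAP 7.8.1, event window: "all adverse events occurring between first drug intakes till 7 days after last drug intake during observation period will be analysed".
- SAP 7.8.1, rate: "Safety will be assessed by treatment exposure time adjusted incidence rate (n in 100 patient years) of ADRs".
- SAP 7.7, extent of exposure: "Only descriptive statistics are planned for this section of the report".
- Protocol 9.7.3: "Several interim analyses will be performed for the purpose of submission of periodic safety reports to PMDA". Protocol 12 adds that further interims may support presentations and publications.

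**The concern.** A rate per 100 patient-years needs one window for both events and time at risk. Here the events stop with the observation period, but the imputed exposure time runs to whatever date the data were cut. For an undated patient beyond week 52, each further day adds to the denominator and nothing to the numerator. The same happens between final contact and the snapshot for a patient known to have been lost, or to have stopped without a date.

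The direction is known: exposure looks longer and the ADR rate looks lower, so the product looks safer. ADR incidence is the primary outcome, and the interims go into periodic safety reports to the authority. For a patient still on treatment and inside the 52 weeks, the snapshot date is ordinary censoring and nothing is wrong.

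**Working it through.** The plan gives no exposure total or ADR rate, so there is no stated figure to reproduce. The check asks when the rule can add time beyond week 52, and how much.

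**Inputs from the documents.** Data collection starts 15 January 2019 (Protocol 6). Registration runs from January 2019 to January 2020 (Protocol 9.2.2.2). Follow-up is 52 weeks = 364 days. Data collection was planned to end 30 April 2021 (Protocol 6). The SAP is dated 24 May 2021 (SAP 10).

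**Assumptions.** Treatment starts are spread evenly from 15 January 2019 to 31 January 2020 (381 days). There is no loss or early stopping. A share *s* of patients has no last-intake date: 5–20%, with 50% as an extreme. The documents give no value for *s*.

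**When the rule can bite.** The first patient reaches day 364 on 14 January 2020 and the last on 29 January 2021. A snapshot up to 14 January 2020 adds no time beyond week 52. From 29 January 2021 every patient is at or past day 364.

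**Formula.** Let T be the time from start to snapshot. Exposure within the observation period is min(T, 364). Under SAP 6.6 an undated patient contributes T. Let k be the extra time divided by the true time if every patient were undated. Then

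reported rate / true rate = 1 / (1 + s × k).

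**By hand, snapshot 24 May 2021.**
- The last starter has T = 479 days, an excess of 479 − 364 = 115. The first has T = 860, an excess of 860 − 364 = 496.
- Mean excess = (115 + 496) / 2 = 305.5 days, so k = 305.5 / 364 = 0.839.
- s = 5%: 1 / (1 + 0.05 × 0.839) = 0.960, which is 4.0% too low.
- s = 20%: 1 / (1 + 0.20 × 0.839) = 0.856, which is 14.4% too low.
- A true rate of 10 per 100 patient-years would show as 9.6 and 8.6.

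**Other snapshots.** Percentage by which the rate is too low:

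| Snapshot | Patients past week 52 | k | s = 5% | 10% | 20% | 50% |
|---|---|---|---|---|---|---|
| 30 Sep 2019 | 0% | 0 | 0 | 0 | 0 | 0 |
| 31 Mar 2020 | 20% | 0.032 | 0.2 | 0.3 | 0.6 | 1.6 |
| 30 Sep 2020 | 68% | 0.258 | 1.3 | 2.5 | 4.9 | 11.4 |
| 30 Apr 2021 | 100% | 0.773 | 3.7 | 7.2 | 13.4 | 27.9 |
| 24 May 2021 | 100% | 0.839 | 4.0 | 7.7 | 14.4 | 29.6 |
| 30 Sep 2021 | 100% | 1.194 | 5.6 | 10.7 | 19.3 | 37.4 |

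The rows before 24 May 2021 apply only if earlier interims used the same rule. The ceiling, with every patient undated, is 1 − 1/1.839 = 45.6% at 24 May 2021. The share *s* therefore drives the size far more than the exact snapshot date does.

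**The case against.** The strongest reply is that SAP 6.6 may be calculating a real quantity. The main limb of Protocol 9.3.1 runs to the last administration and has no 52-week limit of its own; the observation-period wording qualifies only the bracketed alternative. A patient still taking the tablets at the snapshot really has been treated that long. That stands for duration of use as such. It does not help a rate whose events are confined to the observation period.

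Other text points away from a hard stop at day 364. The last window in SAP Table 6.7:1 runs to the end of the study, Protocol Annex 2 calls its time points approximate, and SAP 7.8.1 tabulates first ADR onset in a band beyond 52 weeks and merges a second source of adverse events. If later ADRs are in fact counted, the bias is smaller, but the written limits for events and for exposure then disagree.

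Some of the plan is not visible. SAP 6.1 leaves treatment set-up to the analysis data set plan, and the safety entry in SAP 6.6 shows no text. A cap may sit in either place. Start and end dates of treatment are collected (Protocol 9.3.3), so the undated group may be small; the documents do not say whether a patient still on treatment at week 52 receives an end date.

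A reader might infer three stronger things that the documents do not support:
- *That every interim is biased.* Snapshots up to about 14 January 2020 add no time beyond week 52, and later ones do so only through undated patients.
- *That interim reports will carry a diluted rate.* No passage says that the patient-year rate is produced at interims, and the only SAP shown postdates planned data collection.
- *That SAP 4 is wrong where it says* "No change has been made in the planned analyses from the statistical methods described in the NIS Protocol". SAP 3 ties the plan to Protocol 9.7, which has no rule for last-intake dates, so SAP 6.6 can be read as added detail.

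**Conclusion.** The point holds in limited form and is minor. As written, SAP 6.6 lets interim exposure run past the observation period for undated patients who are beyond week 52 or known to have stopped or been lost, while the event window does not follow. Interim exposure duration would be too long for those patients, and an interim ADR rate per 100 patient-years, if reported, would be too low.

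The 4–14% figure is an illustration. It rests on an assumed 5–20% undated share, even entry, no loss, and a snapshot placed at the SAP date for want of any stated date. On the planned dates, any snapshot taken under this SAP falls after every patient's week 52, so wherever the rule is then used it adds out-of-period time. The crude ADR proportion and the final analysis are not touched by this sentence.

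**What to change.** In SAP 6.6, at interims, impute a missing last-intake date as the earlier of the snapshot date and the end of the patient's 52-week observation period. For patients documented as lost, or as stopped without a date, use the final contact date from Protocol 9.3.1. Define the last day of the observation period. Apply the same upper limit to recorded exposure time and to the ADRs counted in the rate, and reconcile this with the onset band beyond 52 weeks in SAP 7.8.1. If the analysis data set plan already holds such a cap, state it in SAP 6.6.

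The imputation cap costs one line of SAP text and one line of code. What remains is some excess time for patients who are lost but not yet documented as lost.

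Do not cap everyone at the last visit to remove that remainder. Under Protocol 9.4 adverse events are transmitted at once, but visit data only at weeks 26 and 52 or at discontinuation. With the entry pattern above and the planned days of SAP Table 6.7:1, a last-visit cap would leave 79 of 139 patient-years at 31 July 2019 (rate about 77% too high) and 401 of 521 at 31 January 2020 (about 30% too high).
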